For the feasibility assessment, the study period will start on the date when vaccination with Ad26.COV2.S began in each participating country or the latest date when the individual is registered in the data source (plus 365 days) or born and will end a maximum of 12 months thereafter. Individuals will be followed until the earliest of the following dates: death, end of data availability, individual exit from the data source, or the completion of the period.

Safety Evaluation Study

- For the SCRI design, follow-up starts at the start of the pre-vaccination control window following an AESI specific washout period. Follow-up ends at the earliest of the following: death, end of data availability, individual withdrawal of the study, end of the post-vaccination risk or control window, or receipt of another COVID-19 vaccine. We will compare the Ad26.COV2.S vaccine with active comparators with 1) only 1-dose strategy and 2) a 2-dose strategy.
- For the cohort design, the study period will start at the time when Ad26.COV2.S vaccination starts in each participating country and will end at the end of follow-up. For the cohort design, follow-up starts at the start of each risk window and ends at the occurrence of each AESI, death, end of data availability, individual exits the database, after one year of follow-up, receipt of a COVID-19 vaccine (unexposed cohort only), receipt of a different COVID-19 vaccine from the one granting access to the study (exposed cohorts only). For the vaccine-exposed comparator groups, a second dose of the same corresponding vaccine will be allowed (more details will be provided in the SAP). In a sensitivity analysis, follow-up in the cohort study will be censored upon receipt of other vaccines (non-COVID-19 vaccine). We will compare the Ad26.COV2.S vaccine with active comparators with 1) only 1-dose strategy and 2) a 2-dose strategy. For the subgroup analysis of subjects without COVID-19 at the start of each risk window, patients will be censored if they develop COVID-19 during follow-up.

Variables

Exposure assessment

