 - thrombotic events (microangiopathy including capillary leak syndrome), disseminated intravascular coagulation, deep vein thrombosis, pulmonary embolism, cerebral vein thrombosis, peripheral thrombosis, thrombosis with thrombocytopenia and ischemic strokes, acute coronary syndrome (acute myocardial infarction, unstable angina, and new onset angina),
 - bleeding events including haemorrhagic stroke (no subarachnoid),
 - composite endpoint: Venous thrombosis (including pulmonary embolism and deep vein thrombosis)
 - composite endpoint: Arterial thrombosis (including acute coronary syndrome and ischemic stroke),
 - composite endpoint: stroke (including haemorrhagic and non-hemorrhagic stroke)
 - heart failure, and stress cardiomyopathy.
- The incidence of immune/inflammatory events: encephalitis (including acute demyelinating encephalomyelopathy and meningoencephalitis), Guillain-Barré Syndrome, Bell's palsy, immune thrombocytopenia, thrombocytopenia, transverse myelitis and cardiac inflammatory disorders (including myocarditis and pericarditis) within 1-42 days.
- The incidence of sensorineural hearing loss within 1-60 days.
- The incidence of asthma exacerbation within 1-14 days.

Non-acute events (events expected to be recorded >60 days after vaccination)

- The incidence of new-onset autoimmune thyroiditis, multiple sclerosis, acute aseptic arthritis, and type 1 diabetes mellitus within 1-365 days.

Newly identified AESI may be incorporated into the list of AESI to be investigated by the current study if a safety signal occurs.

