8.1.2. Overview of Study Design for Safety Evaluation Study

Evaluation of safety concerns will be conducted using a retrospective observational study in electronic health care databases of various types in Europe. Eligible individuals will be included in the study from the start of Ad26.COV2.S vaccination in each participating country, and the study will end at the last date of data availability in each database.

For each AESI, the study design of the safety evaluation study will depend on whether the AESI is an acute or non-acute event and follow the decision framework described in the ACCESS template protocols for evaluation of safety events in electronic health care databases ([Dodd 2020](#)).

The primary study design for the evaluation of acute events (events expected to occur within 2, 14, 28, 42, or 60 days of vaccination) will be a self-controlled risk interval (SCRI) design with pre- and post-vaccination control window and for non-acute events (events expected to occur within 365 days) will be a cohort design with concurrent unexposed comparators. Additionally, the cohort analysis will also include two active comparator groups: one viral vector vaccine comparator group (i.e., Vaxzevria[®] [AZD1222] by Oxford/AstraZeneca) and one mRNA vaccine comparator group (i.e., Comirnaty[®] [tozinameran] by Pfizer/BioNTech and/or Spikevax[®] [elasomeran] by Moderna), where possible (pending on the feasibility analysis with a maximum follow-up time of one year).

In sensitivity analyses, an equivalent cohort design will also be used to assess acute events. When it is established that data sources do not capture vaccinations well during the feasibility assessment, we will conduct a sensitivity analysis excluding these data sources from the cohort analysis with non-exposed comparators for the non-acute events, to avoid misclassification of exposure.

Another sensitivity analysis will compare the Ad26.COV2.S vaccine with active comparators (1) a 1-dose strategy and (2) a 2-dose strategy.

Individuals start follow-up at the start of each risk window and end follow-up at the earliest occurrence of latest data availability of the databank, individual exit from the database, completion of the study period, or death. At least one year of enrolment prior to the index date (date of vaccination) will be required to determine whether individuals meet the study criteria and to define baseline characteristics. If more historical data is available, this will be included.

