8.1.2.1. Self-controlled Risk Interval Design (Primary Study Design for Acute Events)

The SCRI design will compare the risk of the AESI in a post-vaccination risk window to a pre-vaccination control window (sensitivity analysis) and post-vaccination control window (main analysis) within the same individual.

The SCRI design will include only individuals in the primary analysis who received at least one first-ever dose of the Ad26.COV2.S vaccine during the study period. Vaccinated individuals enter the study at the date of the start of the pre-vaccination control window. The SCRI design will compare the risk of each outcome during the post-vaccination risk window following the COVID-19 dose with a self-matched control interval that may be prior to vaccination, or after the vaccination risk window, to assess the baseline risk of the outcome. The control window will have the same maximum length as the risk window to minimise time-varying confounding that cannot be measured. In case the follow-up time does not capture the maximum post-vaccination risk or control window due to right censoring, all available follow-up time will be utilized. Follow-up will be censored upon vaccination with another COVID-19 vaccine or end of follow-up. A washout period between the control and risk window will be applied to minimise capturing of prevalent events during the risk window. A post-vaccination control window may induce a bias towards the null when an AESI that was identified during the vaccination risk window, is captured again during the control window due to a re-admission instead of reoccurrence of the AESI. This situation is more likely to be encountered for acute potentially recurring events such as cardiac events (including acute coronary syndrome, myocarditis, pericarditis, arrhythmia, and stress cardiomyopathy). Moreover, due to lag-times in updating the relevant databanks, there is a higher risk that the post-vaccination control window may not capture all events and underestimate the rate of events. Use of a pre-vaccination control window will deal with these issues. In a sensitivity analyses, we will use a pre-vaccination control window and a post-vaccination control window will be used for the main analysis. In a sensitivity analysis, vaccination to other non-COVID-19 vaccines will also be an exclusion and censoring event.

We will also compare the Ad26.COV2.S vaccine with active comparators with 1) only 1-dose strategy and 2) a 2-dose strategy.

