[Figure 1](#) shows the SCRI study design diagrammatically using an example with a risk window and control window of 42 days.

Figure 1: Self-Controlled Risk Interval Design

T is time and T=0 is the index date.

8.1.2.2. Cohort Design (Primary Study Design for Non-acute Events and Sensitivity Analysis Design for Acute Events)

For the primary analysis of non-acute events, a retrospective cohort design will be used to estimate the rate of vaccination with Ad26.COV2.S vaccine, describe the characteristics of these vaccinated individuals and subsequently to estimate the incidence of new-onset autoimmune thyroiditis, multiple sclerosis, acute aseptic arthritis, and type 1 diabetes mellitus after receipt of the vaccine dose and to compare this incidence with that occurring in an unvaccinated matched comparator group, and in two groups of individuals exposed to other types of COVID-19 vaccines (i.e., one viral vector vaccine comparator group vaccinated [i.e., Vaxzevria[®] {AZD1222}] by Oxford/AstraZeneca) and one mRNA vaccine comparator group (i.e., Comirnaty[®] [tozinameran] by Pfizer/BioNTech and Spikevax[®] [elasomeran] by Moderna).

As a sensitivity analysis for acute events, a cohort analysis (following the same approach used in the main analysis for non-acute events) will be conducted.

- **Exposed cohort:** individuals will have received at least 1 dose of Ad26.COV2.S vaccine.
- **Concurrent unexposed cohort:** individuals that have not been vaccinated with Ad26.COV2.S vaccine or any other COVID-19 vaccine at any time prior to the index date (time zero) matched to the vaccinated individual for important characteristics as described in Section 8.7.2.1.
- **Cohort exposed to other COVID-19 vaccines:** individuals will have received at least 1 dose of a viral vector COVID-19 vaccine (i.e., Vaxzevria[®] [AZD1222] by Oxford/AstraZeneca) or an mRNA COVID-19 vaccine (Comirnaty[®] [tozinameran] by Pfizer/BioNTech and Spikevax[®] [elasomeran] by Moderna, respectively).

A sensitivity analysis will compare the Ad26.COV2.S vaccine with the active comparators with 1) a 1-dose strategy and 2) a 2-dose strategy.

In this retrospective cohort design, the start of follow-up will be defined as the time when study outcomes start to be counted. The index date in the exposed cohorts (i.e., recipients of the vaccines)

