8.2.5. Exclusion Criteria

For the feasibility assessment, there will be no exclusion criteria.

Individuals will be excluded from the safety evaluation study if:

- They have been vaccinated with any other COVID-19 vaccines before starting each risk window.

- Record of the specific AESI during the specific corresponding washout periods for the SCRI and cohort analyses. Individuals with such acute diagnoses before the AESI-specific washout periods will not be excluded. For clarification, when one AESI will be investigated, any history or prevalence of other AESIs will not be excluded. [Table 1](#) shows the specific washout periods for each AESI.

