8.3.3. Evaluation of Safety Outcomes

The sponsor has created a list of AESIs based on current knowledge of the Ad26.COV2.S vaccine. [Table 1](#) lists and explains the AESIs to be ascertained in the study with specific risk windows. Background incidence rates for most of the data sources and AESIs are available on the VAC4EU dashboard <https://vac4eu.org/covid-19-tool/>. Definitions and codes are available on Zenodo (<https://zenodo.org/communities/vac4eu/>).

Table 1: AESI-Specific Risk Windows and Washout Periods for Patient Inclusion in the Study

Body System	AESI	Disease-specific washout period before the index date	Disease-specific risk window following the index date
Nervous and central nervous system	Encephalitis, including ADEM and meningoencephalitis	365 days	1-42 days
	Guillain-Barré Syndrome	365 days	1-42 days
	Transverse myelitis	365 days	1-42 days
	Bell's palsy	365 days	1-42 days
	Multiple sclerosis, including optic neuritis	365 days	1-365 days
	Sensorineural Hearing loss	365 days	1-60 days
	Generalised convulsion	365 days (w/o epilepsy) 90 days (w/o non-epileptic seizures)	1-14 days
Immune system	Autoimmune thyroiditis	365 days	1-365 days
	Immune thrombocytopenia	365 days	1-42 days
	Type 1 diabetes mellitus	Any time prior*	1-365 days
	Acute aseptic arthritis	365 days	1-365 days
	Anaphylaxis	90 days	0-2 days
Cardiac system	Cardiac inflammatory disorders, including myocarditis and pericarditis	365 days	1-28 days
	Microangiopathy	365 days	1-28 days
	Heart failure	365 days	1-28 days
	Stress cardiomyopathy	365 days	1-28 days
	Coronary artery disease, including acute myocardial infarction	365 days	1-28 days
	Arrhythmia	365 days	1-14 days
Blood and lymphatic system disorders	Deep vein thrombosis	365 days	1-28 days
	Pulmonary embolism	365 days	1-28 days
	Disseminated intravascular coagulation	365 days	1-28 days
	Non-haemorrhagic stroke	365 days	1-28 days
	Haemorrhagic Stroke	365 days	1-28 days
	thrombocytopenia	365 days	1-28 days
	peripheral thrombosis	365 days	1-28 days
	Sinus thrombosis	365 days	1-28 days
	Thrombotic Thrombocytopenia syndrome	365 days	1-28 days
	Composite: venous thrombosis	365 days	1-28 days
	Composite: arterial thrombosis	365 days	1-28 days
Composite: strokes	365 days	1-28 days	
Renal system	Acute kidney failure	365 days	1-14 days
Hepatic system	Acute hepatic failure	365 days	1-14 days
Respiratory system	Exacerbation of asthma	365 days	1-14 days

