8.7.6. Sensitivity Analyses

Sensitivity analyses will be performed to:

- Assess the risk of AESI within extended disease-specific risk windows for events for which the risk interval is not well known or documented in the vaccine safety literature.
- Assess the impact of data sources that are shown not to capture vaccinations well during the feasibility assessment. In the sensitivity analyses with non-exposed comparators those data sources from the cohort analysis for the acute and non-acute events will be excluded, to avoid misclassification of exposure.
- Excluding and censoring upon the administration of other (non-COVID-19) vaccinations in the SCRI and cohort study (see Section 8.1.2.2).
- Comparing Ad26.COV2.S with active comparators with (1) a 1-dose strategy and (2) a 2-dose strategy in the cohort study.
- Conduct a SCRI analysis using a pre-vaccination control window for all acute AESIs.

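### The SCRI washout is anchored inconsistently: taken literally, Table 1 with section 8.2.5 excludes every case in the pre-vaccination control window

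*Protocol*

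**What the plan says.** Table 1 (protocol section 8.3.3) gives one washout per AESI under the column heading "Disease-specific washout period before the index date". It is 365 days for every acute AESI except anaphylaxis (90 days) and one of the two generalised-convulsion entries (90 days). The index date is vaccination: section 8.1.2 says "At least one year of enrolment prior to the index date (date of vaccination) will be required", and the note to Figure 1 says "T is time and T=0 is the index date".

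Section 8.2.5 excludes anyone with a "Record of the specific AESI during the specific corresponding washout periods for the SCRI and cohort analyses" and refers to Table 1 for the lengths.

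On the control window, section 8.1.2.1 says "The control window will have the same maximum length as the risk window to minimise time-varying confounding that cannot be measured". The longest acute risk window is in section 7: "The incidence of sensorineural hearing loss within 1-60 days". Section 8.7.6 plans to "Conduct a SCRI analysis using a pre-vaccination control window for all acute AESIs", and the stratified row of Table 5 names the pre-vaccination window as well as the post-vaccination one.

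Two other places point to a different anchor. In the abstract, for the SCRI, "follow-up starts at the start of the pre-vaccination control window following an AESI specific washout period". Section 8.2.4.2 requires 12 months of registration before the pre-vaccination control window begins, and it admits cases whose event lies in the control window or the risk window.

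**The concern.** A self-controlled comparison needs cases that can fall in either window. If the washout runs back from vaccination, the pre-vaccination control window sits inside the period in which a record of the event disqualifies the person. The same protocol would then both require control-window cases (8.2.4.2) and remove them (8.2.5).

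At stake is the check that the protocol relies on for its main acute-event analysis. Section 8.1.2.1 concedes that a post-vaccination control window can count re-admissions as new events and can miss events through data lag, and it offers the pre-vaccination window as the answer to both. If that analysis cannot be estimated, the answer is not available. Choosing an anchor after zero counts have appeared would be a post hoc decision, taken in scripts that are distributed to several data sources.

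**Working it through.** **The plan's own SCRI figure.** The protocol gives no figure for the washout itself. Its SCRI power in Table 3 reproduces and is not in dispute. For relative risk 2, 100 cases and equal windows (two-sided 5% level assumed), with p = 2/3:

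- A = 2[p ln 2 − ln 1.5] = 0.1133
- B = (ln 2)² p(1 − p)/A = 0.943
- power = Φ[(√(100 × 0.1133) − 1.96)/√0.943] = Φ(1.45) = 92.6%, as stated.

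This calculation presupposes that cases can occur in both windows.

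**Inputs**

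- Washout length W: 365 or 90 days, counted back from vaccination (Table 1).
- Control-window length L: at most the risk-window length (8.1.2.1), so 3 days (anaphylaxis, days 0–2), 14, 28, 42 or 60 days.
- Buffer b between the windows: not given; section 8.1.3 leaves it to the SAP. Assumed range 0–60 days.

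**Interval check.** With vaccination as day 0, the washout covers days −W to −1 and the pre-vaccination control window covers days −(b + L) to −(b + 1). The window lies wholly inside the washout when b + L ≤ W, that is b ≤ W − L.

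| Window | L | W | Largest b with full coverage |
|---|---|---|---|
| Sensorineural hearing loss | 60 | 365 | 305 |
| 42-day AESIs | 42 | 365 | 323 |
| 28-day AESIs | 28 | 365 | 337 |
| 14-day AESIs | 14 | 365 | 351 |
| Convulsion, 90-day entry | 14 | 90 | 76 |
| Anaphylaxis | 3 | 90 | 87 |

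For every buffer in 0–60 days all rows are fully covered. Beyond the limit the window only begins to leave the washout. It is wholly clear when b ≥ W: 365 days for most AESIs, 90 days for the last two rows.

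**Consequence for the estimate.** With equal windows the conditional Poisson rate ratio is (risk-window cases)/(control-window cases). With zero in the denominator there is no finite estimate.

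**Simulation check.** A 42-day window was simulated with buffers of 0, 14, 28 and 60 days and true rate ratios of 1 and 2.

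- Washout from the index date: 0 control cases kept in all eight runs.
- Washout ending where the control window starts: 156 to 181 control cases kept. Rate ratios were 0.85–1.17 for a true value of 1, and 1.83–2.05 for a true value of 2.

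The second version keeps all control-window cases by construction and does not model earlier history, so it illustrates the interval argument and adds no independent evidence.

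**The two anchors side by side.** Table 1 and 8.2.5 fix the index date. The abstract fixes the start of the control window. Section 8.2.4.2 fits the abstract, but as a data-availability rule it does not itself move the exclusion. Section 8.2.3, the body counterpart of the abstract's sentence, omits the washout clause and refers to Table 1, which defines no control window. The abstract and 8.1.2.1 also use the word washout for the gap between windows, which sections 2 and 8.1.3 call a buffer.

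**The case against.** The strongest reply is that the SCRI-specific text already describes a workable design. The abstract's SCRI bullet puts the washout first, 8.2.4.2 asks for the matching look-back and admits control-window cases, and Table 1's heading is a generic one shared with the cohort. An analyst could well follow the SCRI clauses. This stands to the extent that the fault is a contradiction and the intended design may be sound. It does not remove the fault, because 8.2.5 names the SCRI and refers to Table 1, and those are the operative exclusion rules.

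It can also be said that the failure would be seen. Section 8.7.1.3 has case counts reported by window, so zeros in the control column for every acute AESI would stand out. That is right, and it limits the harm: the result would be an analysis that cannot be estimated, not a plausible but biased ratio.

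Finally, Figure 1 is not available in the text reviewed and may show where the washout sits, and the buffer is left to the SAP. A figure could clarify intent but would not change 8.2.5. The buffer would have to exceed the limits tabulated above to matter.

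A reader might infer that the primary acute-event analysis is emptied. The documents do not support this: the main SCRI uses a post-vaccination control window, for which an index-date washout is appropriate, as it is for the cohort. Nor do they support saying that the pre-vaccination analysis will certainly be empty, because the protocol also contains the other anchor.

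**Conclusion.** The point holds as an internal contradiction that should be fixed. Taken literally, Table 1 with 8.2.5 removes all pre-vaccination control-window cases for every acute AESI. This holds for any buffer up to 76 days in the tightest case (the 90-day convulsion entry), 87 days for anaphylaxis, and 305 days or more wherever the washout is 365 days. That a real buffer would fall below these limits is an assumption, since the protocol gives none.

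The effect is confined to the pre-vaccination SCRI sensitivity analysis and the pre-vaccination part of the stratified SCRI. No primary estimate changes. Because the abstract already carries a workable anchor and the failure would show in the reported counts, this is a repair to make before the final analysis and not a defect that invalidates the design.

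**What to change.** - In Table 1 and section 8.2.5, state that for the pre-vaccination SCRI the washout is counted back from the start of the pre-vaccination control window. Keep the index date as anchor for the post-vaccination SCRI and the cohort.
- Carry the same statement into section 8.2.3, so that it agrees with the abstract.
- In the abstract and section 8.1.2.1, call the gap between the windows a buffer, as section 2 defines it.

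A person with the event in the pre-vaccination control window then stays excluded from the post-vaccination SCRI and enters the pre-vaccination SCRI as a control-window case. A sentence saying so would prevent confusion over differing case counts.

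The cost is a column heading or footnote, one exclusion sentence and a few words elsewhere. Section 8.2.4.2 already requires the 12 months of look-back, so no further data are needed. The programming effort cannot be judged from the documents.

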 - Individuals who have a prior history of thrombotic events and/or thrombocytopenia,
 - Prior COVID-19 infection,
 - Individuals with a prior history (ever) of the specific event more than a year before start of follow-up.

These results will be compared to COVID-19 vaccine unexposed individuals and, to individuals exposed to other types of COVID-19 vaccines (mRNA or adenovirus-based platforms) or compared to a control window within the same individual.

Endpoints

Feasibility Assessment

The endpoints for the feasibility assessment, including a monitoring phase, are:

- Quality assessment of data that has been extracted from the source data banks (completeness, logic and benchmarking between data sources and against external data)
- The number of doses and uptake of different COVID-19 vaccines by calendar time
- The demographic and morbidity characteristics of individuals receiving the different COVID-19 vaccines
- Algorithms for AESI identification (including exacerbation of asthma)
- Incident rates and cumulative incidence (risk) of the selected AESIs and corresponding 95% confidence intervals (CIs), without prespecified risk windows
- Risk factors for AESI.

Safety Evaluation Study

The primary endpoints for the safety evaluation study are to estimate the risk of the selected AESIs listed below among individuals vaccinated with the Ad26.COV2.S vaccine and in corresponding unexposed individuals and individuals exposed to other types of COVID-19 vaccines (split between mRNA platform-based vaccines and adenovirus-based platforms), or during a control window within the same individual.

The contractual agreements with data partners will stipulate the ability to allow newly identified AESIs to be incorporated into the study objectives, and the current protocol that will be used for governance approvals will state that additional AESI may be added. Each data access provider is responsible to inform the appropriate ethics boards of these amendments.

Acute events (events expected to be recorded within 60 days of vaccination).

- The incidence of anaphylaxis within 0-2 days.

- The incidence of generalized convulsion, arrhythmia, acute kidney failure and acute hepatic failure within 1-14 days.
- The incidence of the following events within 1-28 days

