Abbreviations: ADEM = Acute disseminated encephalomyelitis, AESI = adverse event of special interest, All non-acute events are considered to have a washout period of 365 days. * For diabetes mellitus which is a chronic condition we will use any time prior for washout.

Exacerbation of asthma ascertainment will require the definition of an asthma cohort and identifying exacerbations of asthma within that cohort.

The asthma cohort will be defined by having:

- a code for asthma and;
- at least 2 prescriptions for an inhaled corticosteroid within 5 years before the index date.

Among this asthma cohort, an exacerbation of asthma was defined by having:

- At least 1 prescription of a systemic glucocorticosteroid during the defined risk window or;

- At least 1 hospitalisation for asthma during the defined risk window.

The date of this event will be the date of the first prescription of a systemic glucocorticosteroid or the admission date for hospitalisation for asthma, whichever comes first.

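### Table 1 applies its chronic-disease washout only to type 1 diabetes, so long-standing multiple sclerosis and autoimmune thyroiditis can be counted as new-onset events in the primary cohort analysis

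*Protocol*

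**What the plan says.** The non-acute endpoint in Protocol section 7 is "The incidence of new-onset autoimmune thyroiditis, multiple sclerosis, acute aseptic arthritis, and type 1 diabetes mellitus within 1-365 days". The abstract and section 8.1.2.2 repeat the new-onset wording, and section 2 describes a washout as the means of identifying incident cases more plausibly.

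Table 1 in section 8.3.3 gives these rows (washout, then risk window):

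- "Multiple sclerosis, including optic neuritis 365 days 1-365 days"
- "Autoimmune thyroiditis 365 days 1-365 days"
- Acute aseptic arthritis: 365 days; days 1-365.
- Type 1 diabetes: any time prior; days 1-365.

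The footnote states the general rule, "All non-acute events are considered to have a washout period of 365 days", and then the exception: "For diabetes mellitus which is a chronic condition we will use any time prior for washout".

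Section 8.2.5 turns the washout into an exclusion: "Record of the specific AESI during the specific corresponding washout periods for the SCRI and cohort analyses". A secondary objective in section 7, repeated in section 8.7.3 for the cohort design, covers "Individuals with a prior history (ever) of the specific event more than a year before start of follow-up" and places this group inside the main study population.

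**The concern.** The protocol gives a reason for the type 1 diabetes exception, namely that the disease is chronic. The same reason applies to multiple sclerosis and autoimmune thyroiditis, and nothing explains why they are treated differently. For a chronic disease, a year without a code does not show that the disease is absent; it may only show that nobody recorded it that year.

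Someone already ill before vaccination did not become ill because of it. If the next code for that person falls in days 1-365, the analysis gains an event that carries no information about the vaccine. This touches two of the four non-acute events, in the design that is primary for them. In a safety study, a shift towards the null is the error that can hide a risk. If the arms differ in how often they see a doctor, the shift can also create an apparent risk or an apparent protection.

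**Working it through.** **1. Can a prevalent patient enter and be counted?** Take a person diagnosed three years before the index date with no code in the last 365 days.

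| Event | Washout in Table 1 | Excluded under section 8.2.5? |
|---|---|---|
| Type 1 diabetes | any time prior | yes, if the earlier record is in the data |
| Multiple sclerosis, including optic neuritis | 365 days | no |
| Autoimmune thyroiditis | 365 days | no |

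In the last two rows the person is at risk from day 1, and a code in days 1-365 can be taken as the event.

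**2. Does another part of the plan prevent this?**

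- Section 8.1.2 says that longer history will be included where available, but this does not override the washout fixed in Table 1.
- Section 8.3.3.1 allows validation of diagnosis and onset date but does not require it. The same section says record review is not possible at ARS.
- Section 8.7.6 and Table 5 list no analysis with a longer washout.
- Section 8.7.2.1 does not match on contact with care. It is measured (8.3.4) and could be adjusted for (8.7.1.2), but adjustment does not turn a prevalent case into an incident one.

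**3. The plan's own figures.** None concerns the washout. The nearest is Table 2, which reproduces: events per arm = 2 × (1.960 + 0.842)² / (ln U)². For U = 3 this is 13.01. At 100 per 100,000 person-years and 60 days each, 13.01 / (0.001 × 60/365) gives 79,121 with unrounded inputs, as printed. All 16 cells agree. The washout does not enter, so no printed figure is wrong because of it.

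**4. Effect on the IRR.** Let f be the share of comparator-arm events that are re-recorded prevalent cases (assumed; not in the documents), R the true IRR, and d the re-recording rate in the exposed arm relative to the comparator. Then

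observed IRR = R × (1 − f) + d × f.

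Equal re-recording (d = 1):

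| f | R = 1.5 | R = 2 | R = 3 |
|---|---|---|---|
| 0.2 | 1.40 | 1.80 | 2.60 |
| 0.5 | 1.25 | 1.50 | 2.00 |
| 0.8 | 1.10 | 1.20 | 1.40 |

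Here f refers to the comparator arm only. At R = 2 the exposed-arm share is f / (2 − f), that is 11%, 33% and 67%. Over both arms together it is 2f / (3 − f), that is 14%, 40% and 73%.

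Unequal re-recording, no true effect (R = 1, f = 0.5): d = 1.2 gives 0.5 + 0.6 = 1.10; d = 0.8 gives 0.5 + 0.4 = 0.90.

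**5. Effect on power (illustration).** Inputs: 100,000 per arm (the minimum exposed target in 8.5.1, matched 1:1), a full year of follow-up without censoring (assumed), R = 2, d = 1, and a Wald test on the log rate ratio with SE = √(1/e0 + 1/e1), where e0 and e1 are the event counts in the comparator and exposed arms.

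| Assumed true incidence per 100,000 person-years | f = 0 | f = 0.2 | f = 0.5 | f = 0.8 |
|---|---|---|---|---|
| 50 | 97.9% | 96.1% | 88.1% | 56.7% |
| 10 | 43.2% | 38.4% | 28.9% | 15.7% |

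Example at incidence 50 and f = 0.5: e0 = 50/0.5 = 100 and e1 = 150. The SE is 0.129, ln 1.5 / 0.129 = 3.14, and 3.14 − 1.96 = 1.18, giving 88.1%.

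**The case against.** Several points on the other side are fair.

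- **Size.** The share of prevalent events is unknown. It depends on how common the disease is relative to its incidence and on how often a known patient goes a year uncoded and then reappears. The documents give neither, and the two diseases need not behave alike. A reader might infer that a given percentage of events is false; the documents support no such figure.
- **Direction.** A reader might infer that the IRR is certainly diluted. That holds only if re-recording is equal between arms, which the plan does not establish.
- **The prior-history objective.** A reader might take it as proof that these patients are retained. It is written for all events and, read literally, also covers type 1 diabetes, where Table 1 removes everyone with a prior record. It shows that the passages need reconciling, not who stays in for a given disease. Likewise, "Individuals with such acute diagnoses before the AESI-specific washout periods will not be excluded" speaks of acute diagnoses and does not clearly cover these two. The point rests on Table 1, its footnote and the exclusion rule.
- **Automatic miscounting.** A reader might infer that every such patient becomes a case. Section 8.3.3.1 leaves refined algorithms and the rule for the case date to the SAP, and validation could catch some. These may reduce the problem, but none is bound to, and the washout itself is fixed in the protocol.
- **Optic neuritis.** It shares a row with multiple sclerosis, and the chronic-disease argument is less obvious for a single past episode. This bears on how the fix works, not on the inconsistency.
- **Available history.** A long look-back is not documented everywhere. SIDIAP holds data from 2006. PHARMO's 12 years is a network-wide average and its data banks differ. No start date for diagnosis history is given for VID or ARS.

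**Conclusion.** The inconsistency is established from current text: one stated reason, applied to one of three chronic new-onset endpoints. That multiple sclerosis and autoimmune thyroiditis are chronic is general clinical knowledge rather than a statement in the protocol. Followed as written, the plan lets prevalent cases into the primary cohort analysis of two of the four non-acute events, and no required step removes them.

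Confidence is high in the defect and low in its size and direction. The bias is towards the null under equal re-recording and can go either way otherwise. The IRR and power tables are illustrations over assumed values, not estimates for this study.

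**What to change.** In Table 1, set the washout for multiple sclerosis (including optic neuritis) and for autoimmune thyroiditis to any time prior, using all available history as for type 1 diabetes. Reword the footnote so that the 365-day rule no longer claims to cover all non-acute events. Keep 365 days for acute aseptic arthritis. Retain the 365-day version for the two changed rows as a sensitivity analysis. State in sections 7 and 8.7.3 that the prior-history secondary analysis does not apply to these new-onset chronic endpoints, type 1 diabetes included.

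The cost is modest but not nil. The any-time-prior rule is already needed for type 1 diabetes, so programming is small. Slightly fewer events will be counted. People with an old optic neuritis record will leave the combined row even if multiple sclerosis is first diagnosed later; the 365-day sensitivity analysis will help show how much that matters. Look-back will differ between people and data sources, with a 12-month minimum, so its length should be reported by source. Narrowing the secondary objective needs a protocol edit, not only a table change.
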